Statistical Methods: The study will aim to enroll up to 1465 participants, which assumes a 10% screen failure rate, with a final allocation of 659 participants in the treatment arm and 659 in the control arm.

This sample size of ensures a power of 90% at a 2-sided α of 5%, assuming a 1:1 randomization, a placebo rate of 6% (of participants with at least one COVID-19–related medically attended contact, due to increased symptom severity, or incidence of death due to COVID-19 through Day 30) and an assumed relative risk reduction of 65% to 2.4% in the active treatment arms. The statistical test of the null hypothesis of no between-group difference in proportions, as specified

in the primary endpoint, will be tested using a χ^2 test at a two-sided 5% significance level. An interim analysis for futility will be performed after 50% of participants have completed the primary endpoint assessment at day 30. Safety analyses will be performed on the Safety Population, consisting of all participants who are randomized and received study drug, analyzed by actual treatment arm. A more detailed description of the statistical methods can be found in Section 7.

Protocol Title: A virtual Phase 2 randomized, placebo-controlled, double-blind study to evaluate the safety and efficacy of the combination of famotidine and celecoxib as a post-exposure prophylaxis (PEP) for newly-infected COVID-19 patients.

Short Title: LEAP-CT as a post-exposure prophylaxis for newly-infected COVID-19 patients.

Rationale: Please refer to the Master Protocol LDOS-21-001 for a comprehensive background and rationale for this study of a combination of famotidine and celecoxib as post-exposure prophylaxis (PEP) for newly-infected COVID-19 patients.

Overall Design: This is a Phase 2, randomized double-blind placebo-controlled decentralized virtual study in which outpatient participants, newly diagnosed for COVID-19, will be randomized in a 1:1 ratio to one of two study groups (1 treatment group and 1 control group). The study is designed as a virtual trial in that it will be conducted, *in situ*, with home-based participants entering self-assessments via a web-enabled adaptive platform – The participants will be under the oversight of regionally based investigators who will be responsible for study conduct and the review of blinded data on a periodic basis.

Intervention Groups and Duration: The treatment regimen for this study is shown in Table 4.

Regimen	Dose	# of Participants

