7.2. Sample Size Determination

The sample size was estimated assuming that an interim analysis with stopping criteria for futility will be performed after 50% of participants have a primary endpoint assessment at Day 30. The O'Brien-Fleming beta-spending function is used to determine the non-binding futility boundary.

A total of 1318 evaluable participants, defined as part of the Full Analysis population (659 per group) are required to detect a relative reduction in the primary efficacy parameter of 60% in the active treatment arms compared to placebo (from of 6% in the placebo group to 2.4% in the active groups) with 90.0% power and using a two-sided χ^2 -test with 0.5% significance level, assuming variances are pooled, and that continuity correction was not used. Assuming a 10% screen failure rate, 1465 enrolled participants will be required.

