7.3. Populations for Analyses

For purposes of analysis, populations are defined in Table 8.

Population	Description
Enrolled	All participants that have signed the Informed Consent Form, met the eligibility criteria, were randomized to study intervention, discontinued before first intake (Screening failures) or received at least one of study medication (Intent-To-Treat (ITT), Safety)
Full Analysis (FAS)	All participants who were randomized and received at least one dose of study medication. Participants in the FAS/ITT will be analyzed as randomized.

Table 8:Analysis Populations

Population	Description
Per Protocol (PP)	All participants who were included in the ITT, completed at least the 30-day assessments, and had no major protocol deviations that could have an influence on the primary efficacy endpoint. Participants in the PPS will be analyzed as treated.
Safety	All participants randomly assigned to study intervention and who take at least one dose of study intervention. Participants will be analyzed according to the intervention they actually received.

Participants excluded from the analysis sets mentioned above will be determined during the Blinded Data Review (BDR) and reasons for exclusions will be documented in the BDR report.

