7.4.2. Efficacy Analyses

The **primary efficacy** endpoint, the percentage of patients with at least one COVID-19–related medically attended contact, due to increased symptom severity or death (all-cause mortality) through Day 30, will be analyzed using a two group χ^2 test with pooled variances and no continuity correction. Statistics and the associated 95% confidence interval will be provided. The primary efficacy analysis will be performed using the ITT and will be repeated for robustness purposes with the PP.

In case of missing data of the primary endpoint at day 30 (Visit 4), the primary analysis will consider participants (with missing primary endpoint data until day 30) as having at least one medically attended visit. For sensitivity purposes, the primary efficacy analysis will be repeated by excluding participants with missing primary endpoint until day 30 (Complete Case Analysis).

The **secondary safety endpoints**: Incidence of Related Serious Adverse Events (SAE), Incidence of discontinuation due to related SAE and Incidence of death will also be analyzed using a χ^2 test. Descriptive statistics including exploratory confidence intervals/p-values will be provided.

All **other efficacy endpoints** will be analyzed in an exploratory manner by applying appropriate statistical methods (e.g. χ^2 test for incidences, log rank test and Kaplan Meier method for cumulative incidences, ANOVA for continuous variables) using the FAS set. Descriptive statistics including exploratory confidence intervals/p-values will be delivered.

All **other safety related endpoints** will be analyzed in a descriptive way by providing descriptive statistics and/or shift tables from baseline to the assessment visits.

For more details of the statistical analysis, methods/models refer to the SAP.

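### Counting missing as an event in both arms is not conservative at these event rates: it turns about 94% of any excess of missing data on placebo into apparent benefit, and it costs power even when missing data are balanced

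*Protocol*

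**What the plan says.** Section 7.4.2 fixes the rule for the primary test: "the primary analysis will consider participants (with missing primary endpoint data until day 30) as having at least one medically attended visit". The rule is the same in both arms. The test itself "will be analyzed using a two group χ^2 test with pooled variances and no continuity correction".

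Two further analyses of the primary endpoint are named there. The first is a complete case analysis: "For sensitivity purposes, the primary efficacy analysis will be repeated by excluding participants with missing primary endpoint until day 30 (Complete Case Analysis"). The second is the per-protocol repeat: "The primary efficacy analysis will be performed using the ITT and will be repeated for robustness purposes with the PP". Section 7.3 limits the per-protocol set to participants who "completed at least the 30-day assessments, and had no major protocol deviations", so it also leaves out those without Day 30 data. The protocol does not say what follows if either analysis disagrees with the primary one.

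Section 7.2 plans for a fall "from of 6% in the placebo group to 2.4% in the active groups) with 90.0% power" with 659 per group. It gives no rate of missing primary endpoint data, overall or by arm. Section 7.4 leaves further missing-data procedures to the SAP.

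**The concern.** Scoring missing as failure is often called conservative. That holds only if the active arm loses at least as many participants as placebo. Here the true event rate is low, so imputed events can rival real ones in number. At 659 per arm the plan expects about 40 events on placebo (0.06 × 659) and 16 on active (0.024 × 659). If 5% are missing in each arm, about 33 participants per arm are scored as events whatever happened to them.

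The comparison then depends heavily on who stopped reporting. More loss on placebo creates benefit, more loss on active hides it, and equal loss dilutes it. Follow-up is remote and rests on daily self-report, so some missing data must be expected. At stake are both the 5% level of the primary test and the 90% power stated for it.

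**Working it through.** **Inputs.** Rates of 6% and 2.4%, 659 per group and 90% power are from section 7.2. The pooled chi-square test without continuity correction is from 7.4.2. The significance level is two-sided 5%: the Synopsis says the sample size "ensures a power of 90% at a 2-sided α of 5" per cent. Section 7.2 prints a different level ("with 0.5% significance level, assuming variances are pooled, and that continuity correction was not used"). Missing rates by arm are assumptions.

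**The plan's own figure.** For 6% vs 2.4% at 90% power, the pooled formula at two-sided 5% gives 651 per group, against 659 stated. Power at 659 is 90.4%. At the printed 0.5% level, 1036 per group would be needed and power at 659 would be 67%. So 659 belongs to 5%, which is used below.

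**Effect of the rule.** Let m be the proportion missing and p the event rate. The analysed rate in an arm is m + (1 − m)p. If p is the same in both arms, the spurious difference is

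(m_placebo − m_active) × (1 − p).

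At p = 6% the multiplier is 0.94. To reach 3.6 points the excess must be 3.6 / 0.94 = 3.83 points, and 0.0383 × 659 is about 25 participants.

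**Chance of a significant result favouring active, no drug effect.** This is Φ[(difference − 1.96 × s0) / s1], where s0 is the pooled and s1 the unpooled standard error of the difference. Worked case, p = 6%, 8% vs 4% missing:

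- placebo 0.08 + 0.92 × 0.06 = 13.52%; active 0.04 + 0.96 × 0.06 = 9.76%; difference 3.76 points
- s0 = 0.01767, s1 = 0.01764
- (0.0376 − 1.96 × 0.01767) / 0.01764 = 0.17, and Φ(0.17) is about 0.57

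| Missing, placebo vs active | Analysed rates (p = 6%) | Difference | Chance, p = 6% | Chance, p = 3% |
|---|---|---|---|---|
| 5% vs 5% | 10.7% vs 10.7% | 0 | 2.5% | 2.5% |
| 6% vs 5% | 11.6% vs 10.7% | 0.9 points | 7.8% | – |
| 6% vs 4% | 11.6% vs 9.8% | 1.9 points | 19.6% | 26% |
| 7% vs 4% | 12.6% vs 9.8% | 2.8 points | 36.9% | 48% |
| 8% vs 4% | 13.5% vs 9.8% | 3.8 points | 56.7% | 70% |
| 10% vs 6% | 15.4% vs 11.6% | 3.8 points | 51.4% | 62% |

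**Power when the planned effect is real and missing data are equal.**

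| Missing in each arm | Analysed rates | Difference | Power |
|---|---|---|---|
| 0% | 6.0% vs 2.4% | 3.6 points | 90% |
| 2% | 7.9% vs 4.4% | 3.5 points | 76% |
| 5% | 10.7% vs 7.3% | 3.4 points | 58% |
| 10% | 15.4% vs 12.2% | 3.2 points | 40% |

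The difference shrinks little. Most of the loss comes from the larger variance at the higher rates.

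**Reverse imbalance.** With the planned effect real, 9% missing on active and 5% on placebo, the rates are 0.09 + 0.91 × 0.024 = 11.2% on active and 10.7% on placebo. The expected difference becomes −0.5 points.

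**What complete case adds.** If missingness is unrelated to outcome, simulation (200,000 runs, 14% vs 10% missing, p = 6%) puts complete case at about 2.5% in favour of active while the primary analysis rejects in 44%. Complete case would then contradict the false result.

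It does not bound outcome-dependent missingness. Take 14% vs 10% missing, a true overall rate of 6% in both arms, and event rates among the missing of 0% on placebo and 20% on active. Complete case sees 0.06 / 0.86 = 7.0% vs (0.06 − 0.10 × 0.20) / 0.90 = 4.4%. The primary analysis sees 0.14 + 0.06 = 20% vs 0.10 + 0.04 = 14%. Complete case favours active in 46% of trials, the primary analysis in 83%, and both together in 44%. These assumptions are deliberately extreme; they show only that agreement between the two analyses is no guarantee.

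**The case against.** The strongest reply has four parts.

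- **Equal dropout is the expectation under a complete null.** In a double-blind trial of a drug that does nothing, missing data are expected to be equal and the error rate is 2.5% per side. Inflation needs a drug that changes reporting without changing medical contacts. This stands. A reader might infer that the 5% level fails as a matter of course; the documents do not support that, and they do not show which way any imbalance would run.
- **The imbalance needed is not trivial.** Matching the planned effect takes about 25 participants. A doubling of dropout, 8% vs 4%, would itself be significant in about 86% of trials and visible in the disposition tables of section 7.4.1. This also stands, although a 1-point excess already raises the error rate to about 7–10% when 0–10% are missing on active.
- **Complete case would expose the artefact.** It would in every row of the first table, since those rows assume missingness unrelated to outcome. But section 7.4.2 attaches no consequence to disagreement, and the per-protocol repeat has the same limit.
- **The SAP may add analyses.** It may. A reader might infer that no planned analysis stresses the result against the drug. The protocol alone cannot show that, and the point does not rest on it: the primary rule is already fixed in 7.4.2.

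A reader might also infer that someone with 29 event-free diary days and no Day 30 entry is scored as an event. Section 7.4.2 does not define missing by diary entries, so the text does not establish this.

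**Conclusion.** The point holds as a conditional one. The rule in section 7.4.2 passes about 94% of any excess of missing data on placebo into the treatment difference. With no drug effect, 2 points of excess (6% vs 4%) raise the chance of a false benefit from 2.5% to about 20%, and 4 points (8% vs 4%) to about 57%. The reverse imbalance can remove or reverse a real effect.

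The power loss needs no imbalance: 90% becomes about 76%, 58% or 40% at 2%, 5% or 10% missing in each arm, and section 7.2 does not allow for it.

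The results rest on 659 analysed per arm, a two-sided 5% level and assumed missing rates. They do not show that the trial will produce a false positive. They show that the stated primary rule can produce or hide the result, and that the protocol ties no efficacy claim to an analysis that would reveal it.

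**What to change.** In section 7.4.2:

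- Prespecify a tipping-point analysis over separate event probabilities for missing participants in each arm. Include the corner in which missing counts as an event on active and takes the observed placebo rate on placebo.
- State that an efficacy claim requires that the result does not rest on the imputed events.

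In section 7.2, state that the 90% power assumes no missing primary endpoint data, or give the power at an assumed missing rate.

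The cost is wording in the protocol and SAP and a few more analysis runs, with no new data. The stated power may look less favourable, and a positive result resting on unequal dropout could no longer be claimed. Replacing the primary handling with multiple imputation is optional and not part of this fix: it brings its own missing-at-random assumption and would have only about 16 to 40 events per arm to model.

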Study Day		Day 1 Baseline/ Start of Treatment ⁴	Day 7(±1)	Day 14 (±1)	Day 30(±1) End of Treatment	Day 60	Day 90
Informed consent ⁵	Х						
Inclusion and Exclusion criteria	Х	Х					
Demographics	Х						
Medical History, including weight reporting ⁶	X						
Concomitant medication review	X	X	X	X	Х		
Blood draw for comprehensive metabolic panel (mobile phlebotomy & laboratory service)	Х		X	X			
Nasal swab for confirmatory PCR test for at-home antigen positive test prescreened participants (mobile phlebotomy & laboratory service)	X						
Randomization and initiation of drug shipment ⁷	Х						
Review of reported baseline symptoms		Х		X			
Confirmation of Study Drug Receipt & Initial Dose		X					
Confirmation of Study Drug Return Shipment ⁸					Х		
Review of eDiary for study drug compliance ⁹			X	X	Х		
Adverse Events Review		X	X	X	Х		
Participant Intake of study drug		Daily on Day	s 1–14				

Study Activities and Assessments	Screening & Randomization ¹		Treatment Po	eriod		Observati	on Period ²
Visit Number ³	1	2	3	4	5	6	7
Study Day		Day 1 Baseline/ Start of Treatment ⁴	Day 7(±1)	Day 14 (±1)	Day 30(±1) End of Treatment	Day 60	Day 90
Symptom questionnaires, spO2, and temperature		Daily for the entire treatment and observation period (Days 1–90)					
Mobile ECG		Х	Х	Х			

¹ Participant will complete demography, medical history, concomitant medications, and questions regarding inclusion and exclusion criteria [including results of SARS-CoV-2 PCR test and self-administered urine pregnancy test] via Site will review participant responses and confirm information with participant by Visit 2.

² During the observational period, while participant is not taking any IP, participant will record long term symptoms for Covid-19, but will be directed to consult with his/her primary care physician (PCP) for follow up of any health changes. Planned contacts with participants on Days 60 and 90 will be performed by study support staff only to confirm continued participation in the study.

³All participant visit activities will be performed remotely.

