5.2. Baseline and Enrollment

Adherence to the study design requirements, including those specified in the SoA, is essential, and required for study conduct.

The following will be performed/collected at Baseline/Day 1:

- Concomitant medication review
- Review of reported baseline symptoms
- Confirmation of Study Drug Receipt & Initial Dose
- Adverse Event Review
- Participant Symptom, SpO2, mobile ECG, & Temperature reporting

Eligibility to continue with dosing of study drug will be confirmed by the Investigator, at Baseline. Should a participant be found to have become ineligible at this time, it will be noted in and the participant discontinued from the study as a Screen failure.

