5.9. Pharmacokinetics/Pharmacodynamics

Pharmacokinetic and pharmacodynamic parameters are not evaluated in this study.

6. **EXPLORATORY ENDPOINTS**

6.1. Exploratory Endpoints: Tracking participants' self-assessments on multiple dimensions.

Patient Recorded Outcomes (PRO) for symptom severity: Participants will select personally relevant COVID-19 symptoms from a list and track the severity of each on a daily basis before and after start of treatment using an 11–point NRS ranging from "None" to "Extreme". After 15 days, participants will continue to complete brief daily and weekly diaries for a total of 3 months following first day of treatment. The list of symptoms will initially contain typical COVID-19 symptoms but will enable participants to add other symptoms that emerge that they attribute to their illness.

Endpoints: The presence, severity and duration of COVID-19 signs and symptoms. Specific metrics include assessing the slope, time course, and extent of change in the mean severity score of various subsets of endorsed symptoms from prior to onset of treatment to specified post-treatment days (e.g., Days 3, 7, 11, 15) and to specified clinical milestones (e.g., sustained clinical recovery).

Hypotheses: The patient population consists of recently PCR-tested individuals who have begun to show one or more cardinal symptoms of COVID-19. Based on published epidemiological surveys the symptoms experienced by outpatients will typically persist over about 4–8 days, with some participants showing an initial period of symptom escalation, and another subset experiencing deterioration of their clinical status around day 7–15, potentially requiring hospitalization. Moreover, a significant minority of participants will report some degree of enduring symptoms over the course of the ensuing weeks to months. We hypothesize that the daily trend following treatment will differ between the treatment groups and the placebo group with a faster and steeper decline in symptom severity scores after treatment and with significantly greater proportional improvement across symptoms with treatment than with placebo. We hypothesize that any early trend towards increasing severity will invert sooner following treatment for key symptoms pertaining to everyday performance (difficulty breathing, myalgia and fatigue) will differ significantly and by more than 50% between treatment and placebo groups.

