Purpose: To demonstrate the utility of participants' self-assessed symptom severity ratings to measure the degree and time course of clinical improvement and differentiate between treatment and controls groups.

PRO for impact of illness on performance: Participants will respond daily to three functional queries, on an 11–point NRS ranging from "No Limitations" to "Extreme Limitations", tracked daily before and after start of treatment. The three discrete dimensions of impact of treatment on capability to perform are: impaired ability to perform my essential tasks and duties; impaired ability to care for myself without assistance, and impaired ability to assist others.

Endpoints: The presence, extent and duration of COVID-19-related functional impairments. Specific metrics include assessing the slope, time course, and extent of change in the three impairment scores from prior to onset of treatment to specified post-treatment days (e.g., Days 3, 7, 11, 15) and to specified clinical milestones (e.g., sustained clinical recovery).

Hypotheses: We hypothesize that the daily trend following treatment will differ between the treatment and placebo groups with a quicker and steeper decline in functional impairment scores with significantly greater proportional improvement with treatment v. placebo (the treatment group will improve faster than the control group). We hypothesize that any existing trend towards increasing functional impairment will invert earlier following treatment than with placebo. We hypothesize that the 7–day AUC of functional impairment scores post treatment will differ significantly and by more than 50% between treatment and placebo groups.

Purpose: To demonstrate the utility of participants' self-assessed impairment ratings in capturing the degree and time course of improved real-world performance and differentiate between treatment and control groups.

6.2. Participant Protocol Debrief: Participants will respond to a trio of probes.

 Participants will generate retrospective assessments of their overall degree of improvement at Day 15 following onset of treatment and at termination of participation using the PGIC (Patient's Global Impression of Change) scale, an established, widelyused 7-point qualitative rating scale of perceived treatment efficacy ("very much improved," "much improved," "minimally improved," "no change," "minimally worse," "much worse," or "very much worse.").

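### The only method named for continuous exploratory endpoints is ANOVA; for PRO change from baseline, adjusting for the pre-dose rating would gain precision from data already collected

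*Protocol*

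**What the plan says.** Protocol Section 7.4.2 states that the efficacy endpoints other than the primary "will be analyzed in an exploratory manner by applying appropriate statistical methods". It then lists examples in brackets: a chi-square test for incidences, log-rank and Kaplan-Meier methods for cumulative incidences, and "ANOVA for continuous variables". The Full Analysis Set is used, and confidence intervals and p-values are promised on an exploratory footing. The section closes with "For more details of the statistical analysis, methods/models refer to the SAP".

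Section 6.1 describes the continuous PRO metrics. For symptoms they include "extent of change in the mean severity score of various subsets of endorsed symptoms from prior to onset of treatment to specified post-treatment days". For function they include "extent of change in the three impairment scores from prior to onset of treatment to specified post-treatment days". Slope and time course are listed alongside change, and the example days are 3, 7, 11 and 15.

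On the covariate, Section 6.1 says that the impairment ratings are "tracked daily before and after start of treatment", and it describes symptom severity in the same way. Table 5 schedules the symptom questionnaires daily from Day 1 to Day 90. Section 5.2 lists "Review of reported baseline symptoms" and the initial dose among the Day 1 activities, without giving their order.

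**The concern.** An outcome defined as change from a pre-treatment rating has an obvious covariate, which is that rating. A plain ANOVA on change subtracts the baseline with a slope fixed at 1. A plain ANOVA on the follow-up score ignores the baseline altogether. ANCOVA estimates the slope from the data. In large samples it is at least as precise as either, and it removes the part of any chance baseline imbalance that the fixed slope handles wrongly.

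The precision has some use here. Section 6.1 attaches hypotheses to these exploratory endpoints: significantly greater improvement with treatment and, for function, a 7-day area under the curve that differs by more than half. The example that the protocol chose for continuous data is the less efficient one, and it is what the SAP author would start from.

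**Working it through.** **Inputs.** From the protocol: 659 participants per group (Section 7.2). Not in the protocol: the correlation *r* between the pre-dose and follow-up ratings, and the variances at the two times. I assume *r* from 0.3 to 0.8 and, at first, equal variances.

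**The plan's own figure.** The protocol gives no power or precision figure for the PROs. Its only sample size is for the binary primary endpoint. For 6% against 2.4%, two-sided 5%, 90% power, pooled variance and no continuity correction:

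n = [1.960 × √(2 × 0.042 × 0.958) + 1.282 × √(0.06 × 0.94 + 0.024 × 0.976)]² / 0.036² = 651 per arm.

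This is within about 1% of 659, and 659 per arm gives 90.4% power. (The 5% level is that of the Synopsis and Section 7.4.3; Section 7.2 prints 0.5%, which would need 1036 per arm. That is a separate matter.) Nothing in this calculation depends on how the PROs are analysed. It only supplies n.

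**Variance of the treatment effect.** In units of 2σ²/n:

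- ANOVA on change: 2(1 − r)
- ANOVA on the follow-up score: 1
- ANCOVA: 1 − r²

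Hence ANCOVA / change = (1 − r²) / [2(1 − r)] = (1 + r)/2, and ANCOVA / follow-up = 1 − r².

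The detectable difference at 90% power, in SD units, is (1.960 + 1.282) × √(2V/659), with V taken from the list above. If an effect has 80% power under ANOVA on change, its power under ANCOVA is Φ{(1.960 + 0.842)/√[(1 + r)/2] − 1.960}.

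| r (assumed) | ANCOVA / change | ANCOVA / follow-up | Detectable difference, change → ANCOVA | Power under ANCOVA where change has 80% |
|---|---|---|---|---|
| 0.3 | 0.65 | 0.91 | 0.211 → 0.170 | 93.5% |
| 0.5 | 0.75 | 0.75 | 0.179 → 0.155 | 89.9% |
| 0.7 | 0.85 | 0.51 | 0.138 → 0.128 | 86.0% |
| 0.8 | 0.90 | 0.36 | 0.113 → 0.107 | 84.0% |

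A simulation at 659 per arm with 2,000 replicates gave ANCOVA / change ratios of 0.65, 0.77 and 0.85 at r = 0.3, 0.5 and 0.7, in line with the formula.

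**If the variances differ.** Let k be the baseline SD divided by the follow-up SD. The variance of change is then 1 + k² − 2rk = (1 − r²) + (k − r)², in units of the follow-up variance. The ratio (1 − r²) / [(1 − r²) + (k − r)²] can never exceed 1, so the direction does not depend on equal variances, but the size does. At r = 0.5, for example, k = 2 gives 0.75/3 = 0.25, k = 1 gives 0.75, and k = 0.5 gives 0.75/0.75 = 1, which is no gain.

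**The case against.** The strongest objection is that the protocol does not fix this analysis. ANOVA follows an e.g., it is not tied by name to the PRO change scores, the endpoints are exploratory, and models are left to a SAP that is not shown. All of that is correct, and it limits the point to a suggested improvement. What remains is that the protocol is not silent. It offers one method for continuous endpoints, and a better one is available at no data cost.

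A reader might go further than the text allows in four ways:

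- *That the protocol commits to unadjusted ANOVA of PRO change scores.* It does not. Change is one of several metrics in Section 6.1, which names no test, and nothing in Section 7.4.2 rules out a covariate or a repeated-measures model.
- *That the baseline is thrown away or the result biased.* A change score already uses the baseline, with slope 1, and randomization keeps ANOVA unbiased. Only part of the available precision is lost.
- *That baseline severity is known to vary widely.* The protocol gives no SD. A wide spread is plausible, because one symptom is enough for entry and dosing waits on shipment, but that is an inference.
- *That the Day 1 rating is the right covariate.* Day 1 holds both the first dose and the symptom report, in no stated order, so that rating may be post-dose.

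It is also fair to object that the percentages rest on an assumed correlation and on equal variances. Section 6.1 expects outpatient symptoms to last about 4 to 8 days, so equal variance at Days 11 or 15 is doubtful. The direction survives, as shown in the working, but the percentages are illustrative.

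**Conclusion.** The point holds as a low-cost improvement. It is neither an error nor a contradiction. For PRO change from baseline, a baseline-adjusted analysis is at least as precise in large samples as the ANOVA that the protocol offers. With equal variances and r between 0.3 and 0.7, the variance falls by 15% to 35% relative to ANOVA on change. At r = 0.8 the reduction is 10%. These sizes rest on values that the protocol does not give.

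The primary chi-square test, the sample size of 659 per group and the main conclusion of the trial are unaffected. The unseen SAP may already specify an adjusted model, in which case only the protocol's example needs to be aligned with it.

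**What to change.** In Section 7.4.2, for PRO change-from-baseline endpoints, replace ANOVA with: *ANCOVA adjusted for the last pre-dose rating of the same scale, or a repeated-measures model with that covariate.* Carry the same wording into the SAP, which Section 7.4 says is finalized before the interim database lock.

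Two details should go with it:

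- Define the covariate as the last rating before the first dose, and make sure that the data platform can identify it when both fall on Day 1.
- Section 6.1 lets participants add symptoms that emerge later. Those first added after treatment starts have no pre-dose rating, so the SAP should state how they are handled, for example by summarizing them separately from the adjusted comparison.

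The cost is one line in the protocol, a short SAP paragraph and one degree of freedom in the model. No new data are needed beyond the ratings that Section 6.1 already describes.
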